 121 metformin monotherapy.¹¹ Individuals were
 122 randomized in two groups to receive
 123 additional liraglutide up to 1.8 mg sc once
 124 daily or to remain on Metformin. Our results showed that ultrasound measured EAT
 125 thickness decreased from 10.2 ± 2 to 6.9 ± 1.9 and 5.8 ± 1.9 mm ($p < 0.001$) after 12 and 24
 126 weeks, respectively, accounting for approximately 40% of reduction at 12 and 24 weeks
 127 (*graphic on the right*), whereas there was no significant EAT reduction in the Metformin
 128 group. EAT shrunk independently of overall weight loss and improved glucose control. A
 129 milder, as compared to our results, yet noticeable (-13%), reduction of EAT thickness was
 130 recently observed after 12 weeks of treatment either with liraglutide or exenatide in a
 131 smaller group of patients with type 2 diabetes.¹² However, EAT results in this study were
 132 pooled together making difficult to discriminate differences between the two agents.

[figure not shown]

133

[figure not shown]
[figure not shown]
134 **EAT as pro-inflammatory organ:** EAT of CAD subjects is
 135 enriched with pro-inflammatory genes, as our recent microarray
 136 analysis (*microarray table on the left*) showed.⁴ Pro-
 137 inflammatory cytokines are secreted and transported from EAT
 138 into the coronary lumen through vasocrine and paracrine
 139 pathways.¹⁻³

140 We recently showed that diabetic EAT was mainly enriched in
 141 inflammatory genes, such Interleukin-6 (IL-6) (*graphic on the right*)
 142 and Tumor Necrosis Factor-alpha (TNF- α).¹⁷ Our study suggests a
 143 unique and novel atherogenic pathway in diabetes mediated by EAT
 144 inflammatory profile.

145
146 EAT expresses GLP-1 receptor (GLP-1R)

147 Whether EAT expressed GLP-1 receptor (GLP-1R) was unknown.
 148 We recently performed a RNA-sequencing (RNA-seq analysis) and
 149 Quantitative real-time RT-PCR (qRT-PCR) to evaluate the presence
 150 of GLP-1R in EAT obtained from 8 subjects with coronary artery
 151 disease and type 2 diabetes mellitus undergoing elective cardiac
 152 surgery. Immunofluorescence was also performed on EAT and SAT
 153 samples using Mab 3f52 against GLP-1R. RNA-seq analysis showed
 154 that EAT expresses *GLP-1R* gene. qRT-PCR analysis confirmed
 155 GLP-1R expression by using two different sets of intron-spanning
 156 primers (*graphic on the right*). Immunofluorescence showed that
 157 GLP-1R is present and more abundant in EAT than SAT

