234 Liraglutide. The randomized, double-blind, placebo-controlled study design will allow for
235 an independent and unbiased effect of Liraglutide on study results. In addition, actions to
236 equalize weight loss and maintain similar glucose control between study arms will rule out
237 the confounding effects of these factors on the study outcomes.

238 **Specific Objectives**

239 **Primary Objective:**

240 • to test the hypothesis that liraglutide can reduce the pro-inflammatory
241 transcriptome profile of EAT of subjects with T2DM and CAD.

242 **Secondary Objectives:**

243 • to assess the hypothesis that liraglutide will reduce the ultrasound measured EAT
244 thickness in subjects with T2DM and CAD.
245 • to evaluate the hypothesis that liraglutide can produce more anti-inflammatory
246 effects in the EAT as compared to SAT of subjects with T2DM and CAD.
247 • to test the hypothesis that EAT mRNA and protein expression of GLP-1R will be
248 greater in subjects receiving liraglutide as compared to those continuing their
249 standard therapy

250

251 **Research Design and Methods**

252 **Study Hypotheses**

253 **Hypothesis for Primary Objective:** We hypothesize that EAT inflammatory gene mRNA
254 and protein expression will be lower in subjects receiving additional therapy with
255 liraglutide as compared to those who will continue with their current treatment.

256 **Hypothesis for Second Objectives:** based on our biomolecular and clinical preliminary
257 data, we hypothesize that a) EAT thickness will respond and decrease more on liraglutide
258 than on standard therapy, b) inflammatory genes and protein expression will be different
259 in EAT vs SAT c) EAT GLP-1R expression will be greater in patients on liraglutide vs
260 those on standard therapy.

261

262 **Endpoints**

263 **Primary Endpoint:**

264 • Change from baseline in EAT inflammation (measured as mRNA and protein
265 expression of TNF- α and IL-6) within a minimum of 3 and up to 12 weeks of treatment

266 **Secondary Endpoints:** Change from baseline within a minimum of 3 and up to 12 weeks of
267 treatment for the following parameters:

- 268 • Ultrasound measured EAT thickness
- 269 • SAT inflammation (measured as mRNA and protein expression of TNF- α and IL-6)
- 270 • EAT GLP-1R (measured as mRNA and protein expression of GLP-1R)

271 **Study Type**

272 This is an Investigator Sponsored Study (ISS).

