273 This will be a 12-week randomized, double-blind, placebo-controlled interventional study
274 in 40 patients with T2DM and CAD with an acceptable glycemic control on their current
275 diabetes regimen who require elective coronary artery bypass grafting (CABG) regardless
276 of their participation in the study.

277 A minimum time frame of 3-week treatment will be considered to detect significant
278 changes in the study endpoints. If not all subjects would be able to complete the 12
279 weeks, study outcomes will be evaluated at the 3 week time point.

280

281 **Study Design** Study subjects will be randomized in two groups of 20 patients to receive
282 additional liraglutide, (L-group) or to remain on current treatment or placebo (D-group).

- 283 • L-group will be started on liraglutide. Liraglutide will be started and administered
284 for 12 weeks prior to CABG with a starting dose of 0.6 mg (after a least one week)
285 and subsequent increments to 1.2 mg (after a least one week) and to 1.8 mg (after
286 at least a week on 1.2 mg). The dose of 1.8 mg daily will be maintained until the
287 end of the 12-week study. Other and current diabetes treatment will be continued.
288 In those study participants who may be impacted by CABG scheduling and
289 COVID-19, and cannot complete the 12-week treatment, we will consider a
290 minimum time frame of 3 weeks to detect significant changes in the study primary
291 endpoints.
- 292 • D-group: placebo will be administered in addition to current treatment prior to the
293 CABG with a starting dose of 0.6 mg (after a least one week) and subsequent
294 increments to 1.2 mg (after a least one week) and to 1.8 mg (after at least a week
295 on 1.2 mg). Patients will be started on a supervised diet to achieve approximately
296 5% of weight loss between 3 and 12 weeks. In those study participants who may be
297 impacted by CABG scheduling and COVID-19, and cannot complete the 12-week
298 treatment, we will consider a minimum time frame of 3 weeks to detect significant
299 changes in the study primary endpoints.

300

301 Ultrasonographic measurement of EAT thickness will be performed at baseline and
302 after 12 weeks in all patients, regardless of the study arm.

303 All groups will receive lifestyle and diabetes education, and supervised diet as
304 part of the standard care, to insure similar glycemic control between arms and
305 weight loss. Study patient will be also required to check and log their finger stick

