480 correlation coefficient. Inter- and intra-observer reproducibility will be evaluated by the
481 intra- class correlation coefficient in all subjects. Echocardiograms will be read by Dr
482 [name] and an experienced cardiac imaging technician. Previously published studies
483 have shown that intra- and inter-observer reproducibility of epicardial fat measurement was
484 excellent. Intra-class correlation coefficients varied from 0.90 to 0.98 and from 0.93 to
485 0.98, respectively indicating good reproducibility and reliability. Both readers will be
486 blinded to the subjects' clinical data.

487 **Anthropometrics and Clinical measures:** As standard of care, height (in cm) and weight
488 (in kg) will be measured, and BMI will be calculated. Waist circumference (in cm or
489 inches) will be measured as the minimum circumference between the lower rib margin and
490 the iliac crest. Blood pressure will be also measured.

491 **Blood Measurements:** Lipid panel, lipase, and amylase are not study end-points and will
492 be collected if made available through a standard of care procedure at baseline and after 4
493 or 12 weeks.

494 **Low calorie Diet (LCD)** A low calorie diet program will be prescribed to study patients
495 and controls. A RD who will reach out to patients to insure adherence to the dietary
496 program will supervise the LCD. This will help patients to achieve approximately 5% of
497 weight loss between 3 and 12 weeks.

498 **Assessments for Safety**

499 **Potential Risks to the Subjects**

500 The risks of this study are minimal are mainly related to risks associated with the
501 investigational drug liraglutide, echocardiogram, blood draw, and a potential breach of
502 confidentiality.

503 **Drug therapy:** liraglutide, (Victoza®), is a GLP-1A indicated as an adjunct to diet and
504 exercise to improve glycemic control in adults with T2DM. Liraglutide is taken once daily
505 at any time of day, without regard to the timing of meals. Liraglutide is injected

506 subcutaneously in the abdomen, thigh, or upper arm. Liraglutide may cause mild and
507 usually well-tolerable gastro-intestinal side effects (5%), such as nausea, constipation.
508 Liraglutide is contraindicated in patients with a personal or family history of medullary
509 thyroid cancer and in patients with Multiple Endocrine Neoplasia (MEN). Based on
510 spontaneous postmarketing reports, acute pancreatitis has been observed in patients treated

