602 those patients who will receive treatment only for 3 weeks. The difference in EAT TNF- α
603 and IL-6 between liraglutide treated and placebo treated patients is expected to be
604 approximately 1X fold after 3 weeks of treatment.

605

606 The larger sample proposed in this current project would likely reduce the variability. To
607 further assure consistency of results, mRNA and protein expression values will be log-

608 transformed prior to statistical analyses unless they will be normally distributed.
 609 Housekeeping genes will be also used for both RT-PCR and western blot analyses.
 610 In those patients who will not complete the 12-week treatment, the analysis of EAT genes
 611 from the samples will be time adjusted

612
 613 Statistical power was also calculated to detect statistically significant differences in the
 614 ultrasound measured EAT thickness, secondary endpoint, between the two study arms Our
 615 group very recently showed that additional therapy with liraglutide for 12 weeks caused a
 616 reduction in ultrasound measured EAT from 9.6 ± 2 to 6.2 ± 1.5 mm ($p < 0.001$) in 54 patients
 617 with T2DM ¹¹. Given the reference value and the expected difference in EAT, the
 618 statistical power of the study (two-sided, $\alpha = 0.05$) was calculated.

619

Outcome	Reference value \pm SD	Expected Difference	Detectable difference with 80% power $\alpha = 0.05$	Detectable difference with >99% power $\alpha = 0.05$
EAT (mm)	9.6 ± 2	-20-or -30%	-20% (absolute difference = 1.9)	-30% (absolute difference = 2.88)

620

621 Assuming a difference of approximately 2 mm (20%) in EAT to be clinically significant
 622 (based on our recent and previously published data ¹⁰⁻¹⁴), a convenience sample of 20
 623 individuals for each group will therefore provide at least the statistical power (80%) to
 624 detect an expected difference of at least -20% in the EAT before and after treatment with
 625 liraglutide. Baseline standard Deviation (SDs) of 2 is expected to lower to approximately
 626 1.5 for the expected change. The expected change of SD will further assure significant
 627 statistical power of the comparative test.

628

629 In those study patients who will not be able to complete the 12-week treatment, we
 630 anticipate to see a 15% of EAT reduction after 3 weeks in patients who will be allocated to
 631 liraglutide. This anticipated 15% of EAT reduction will remain clinically significant. For

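### The EAT-thickness power enters a before/after fall on liraglutide as the between-arm difference, states no control-arm change, and does not say whether 20–30% is a total or a net effect

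*Combined protocol and SAP*

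**What the plan says.** The Power Analysis introduces the thickness calculation as one for "ultrasound measured EAT thickness, secondary endpoint, between the two study arms". The only effect data it cites are from one arm of the group's earlier study: 9.6 ± 2 to 6.2 ± 1.5 mm after 12 weeks on liraglutide. The table lists an expected difference of 20% or 30%, with 1.9 mm detectable at 80% power and 2.88 mm at >99%. The text concludes that 20 per group can "detect an expected difference of at least -20% in the EAT before and after treatment with" liraglutide. It expects the SD to drop from 2 to about 1.5 mm. It gives no expected change for the placebo arm.

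Other sections bear on this:

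- Study Hypotheses: the claim is comparative, "data, we hypothesize that a) EAT thickness will respond and decrease more on liraglutide" than on standard therapy.
- Study Design, D-group: "Patients will be started on a supervised diet to achieve approximately" 5% weight loss. The same section extends the supervised diet to all groups.
- Low calorie Diet: "A low calorie diet program will be prescribed to study patients" and controls.
- Study Rationale: steps to "equalize weight loss and maintain similar glucose control between study arms will rule out" confounding by those factors.
- Preliminary Data: in the earlier study EAT fell on liraglutide, independently of weight loss according to the protocol, "whereas there was no significant EAT reduction in the Metformin" group.
- End of Statistical Considerations: the one sentence that names a test for thickness describes a t-test of values before and after treatment.

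**The concern.** A before/after fall in one arm and a difference between arms are different quantities. They coincide only if the control arm does not move, or if the quoted fall is already net of whatever the control arm does. The plan states neither.

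The question is live here because the diet is given to both arms. A total fall on liraglutide would contain any diet effect, and the control arm would show that effect too. The plan also gives some reason to expect a control fall: it treats weight loss as a possible confounder of the study outcomes and says that echocardiographic EAT reflects visceral fat.

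At stake is what the 80% refers to. If it belongs to a total fall, the power for the comparative hypothesis is lower. A null result could then be read as stronger evidence against a drug effect than the design supports.

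**Working it through.** **Inputs.** From the Power Analysis: two-sided alpha 0.05, 20 per arm, reference 9.6 mm, SD 2 mm (or 1.5 mm), effects of 20% (1.92 mm) and 30% (2.88 mm), and a cited fall of 9.6 − 6.2 = 3.4 mm (3.4/9.6 = 35%). Control falls of 1%, 5% and 10% are my assumptions, because the documents give none.

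**Formula.** Two-sample t-test: d = (liraglutide fall − control fall)/SD, noncentrality d × √(n/2), with 2n − 2 = 38 degrees of freedom.

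**Reproducing the plan's figures (control fall zero, SD 2).**

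- 20%: d = 1.92/2 = 0.96, noncentrality 0.96 × √10 = 3.04, power 84.1%. With the rounded 1.9 mm it is 83.3%.
- 30%: d = 2.88/2 = 1.44, noncentrality 4.55, power 99.3%.

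These match the table's 80% (stated as a minimum) and >99%. A one-arm before/after test of 1.92 mm with an SD of change of 2 mm would have noncentrality 0.96 × √20 = 4.29 and power of about 98%. So the stated figures behave as between-arm powers with the whole fall entered as the arm difference.

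**Net difference detectable at 80% power.** With 20 per arm it is 1.82 mm at SD 2 and 1.36 mm at SD 1.5.

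**Power when the stated percentage is the total liraglutide fall.** The difference is the liraglutide fall minus the control percentage × 9.6 mm. For example, 1.92 − 0.48 = 1.44 mm at a 5% control fall.

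| Total liraglutide fall | SD (mm) | Control 0% | 1% | 5% | 10% |
|---|---|---|---|---|---|
| 20% (1.92 mm) | 2 | 84.1% | 80.2% | 60.2% | 31.6% |
| 20% (1.92 mm) | 1.5 | 97.6% | 96.3% | 84.1% | 50.5% |
| 30% (2.88 mm) | 2 | 99.3% | 99.0% | 95.9% | 84.1% |
| 35% (3.4 mm) | 2 | 99.9% | 99.9% | 99.4% | 96.4% |

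**Largest control fall that keeps 80%** (total fall minus detectable net difference):

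- 20%, SD 2: 1.92 − 1.82 = 0.10 mm, about 1%.
- 20%, SD 1.5: 1.92 − 1.36 = 0.56 mm, about 6%.
- 30%, SD 2: 2.88 − 1.82 = 1.06 mm, about 11%.
- 35%, SD 2: 3.4 − 1.82 = 1.58 mm, about 16%.

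**If 20% is the drug effect beyond diet** and the two effects add, the shared diet effect cancels. The difference stays at 1.92 mm and power stays at 84%.

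**Attrition.** At the 10% upper bound given under Subject Compliance (18 per arm), the 20%, SD 2 case has 79.9% power even with no control fall.

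**The case against.** The strongest reply is that both arms get the diet. If the sponsor means 20% as the effect of liraglutide on top of diet, a diet effect cancels and nothing is lost. That is a legitimate reading. The plan does not adopt it, however, and its before/after wording points the other way.

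Second, 20% is modest beside the cited 35% fall, and the plan expects a smaller SD. Both points stand. A reader might infer that the 80% holds only if the diet leaves EAT essentially unchanged. That is true only for a 20% total fall at SD 2; the plan's other figures tolerate control falls of about 6% to 16%.

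Third, the protocol reports that EAT shrank independently of weight loss in the earlier study. This is its most direct statement on the matter and weighs against a large diet effect. It concerns the fall on liraglutide, though, and does not show that a low calorie diet leaves EAT unchanged.

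A reader might also infer that the sizing borrowed the unchanged metformin group as its comparator. The documents do not show this: that result appears only in Preliminary Data, and the power text uses no comparator data.

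Finally, the sentence on t or Mann-Whitney tests of liraglutide against placebo could be read to cover thickness. That is possible, but the only sentence naming thickness describes a before/after comparison.

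**Conclusion.** The point holds as a fault in how the effect and its power are defined. The plan states a between-arm aim, describes a within-arm effect, gives no control-arm change, and leaves open whether 20–30% is total or net.

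The size depends on that choice. If 20% is the total fall and SD is 2 mm, power drops from 84% with static controls to 60% at a 5% control fall and 32% at 10%. At SD 1.5 mm the corresponding figures are 98%, 84% and 50.5%. At a 30% total fall and SD 2, power is 84% or more up to a 10% control fall; at the cited 35% fall it is 96% or more. If 20% is net of diet, 84% stands.

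These figures rest on assumed control falls and on applying the plan's thickness SD to the between-arm contrast, since no SD of change is given. The documents do not support a conclusion that the study is too small. Thickness is a secondary endpoint, and the sizing for the primary endpoint is not touched by this point.

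**What to change.** In the thickness part of the Power Analysis:

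1. Define the effect as the between-arm difference in change in EAT thickness, liraglutide plus diet against placebo plus diet.
2. State that 20 per arm gives 80% power for a net difference of about 1.8 mm at SD 2 mm.
3. Say whether 20–30% is the total fall on liraglutide or the fall beyond diet, and give the expected change in each arm.
4. Show power over a range of control falls (for example 0%, 5% and 10%) for SD 2 and SD 1.5 mm.

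In the closing analysis text of Statistical Considerations, replace the before/after t-test for thickness with a test of the same between-arm contrast, for example a comparison of change with adjustment for baseline thickness. A within-arm before/after summary can remain as description.

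The cost is rewording one paragraph, one table and one sentence. The stated power may become less favourable. No change to sample size, diet or treatment is needed.

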451 will be performed at -35 °C with 12 μ m thickness using a Leica CM1850 UV cryostat
452 (Wetzlar, Germany). The sections will be fixed for 20 min with 4% PFA, washed with PBS
453 and dried at room temperature overnight. Sections will be washed 3 x with PBS and
454 incubated with PBS with 3% BSA and 0.4% triton X for 1 hour. Sections will then
455 incubated with Mab 3f52 (1:50 dilution) antibody overnight in PBS with 3% BSA and
456 0.4% triton X. Sections will be then washed 4 times with PBS and incubated with
457 biotinylated anti mouse IgG for 1 hour at room temperature, washed 4 times with PBS,
458 then incubated at room temperature with horseradish peroxidase-streptavidin for another
459 hour, washed 4 times with PBS and then incubated at room temperature with alexa fluor
460 647 tyramide for 10 min. Sections will be further washed 3 times and incubated with DAPI
461 (Thermo fisher, Waltham, MA) for 30 min. The samples will be washed 3 times with PBS
462 and mounted on Mowiol 4-88 (Sigma-Aldrich, St Louis, MO). The tyramide signal can
463 amplify from 10 to 200 times the immunofluorescence signal from low expressed proteins
464 (Molecular probes, Eugene, OR). The fluorescence images will be acquired using a Zeiss
465 LSM 710 confocal microscope (Oberkochen, Germany).

466 **Echocardiographic EAT Thickness:**

467 Echocardiogram for EAT thickness measurement will be performed at baseline and after
468 12 weeks in all patients, regardless of the study arm. EAT thickness will be measured
469 according to the method firstly described and validated by [name] ⁷⁻⁸. Briefly, EAT will
470 be identified as the echo-free space between the outer wall of the myocardium and the
471 visceral layer of pericardium. EAT thickness will be measured perpendicularly on the free
472 wall of the right ventricle at end-systole in three cardiac cycles. Parasternal long views
473 allow the most accurate measurement of EAT on the right ventricle, with optimal cursor
474 beam orientation. Maximum epicardial fat thickness will be measured at the point on the
475 free wall of the right ventricle along the midline of the ultrasound beam, perpendicular to
476 the aortic annulus, used as anatomical landmark for this view. The average value of three
477 cardiac cycles will be considered.

478 ***Reliability of echocardiographic measurement of EAT***

479 Reliability of echocardiographic measurement of EAT will be assessed by the intra-class

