 632 example, a EAT thickness of 10 mm may likely decrease to 8.5 mm after 3 weeks of
 633 treatment with liraglutide, a clinically meaningful change for the patient cardio-metabolic
 634 profile.

635

636 This sample size also considers the difficulties with recruitment in the real world clinics.
 637 Based on our previous studies in humans, some participants may be lost to follow-up.

638

639 Student's t-test or non-parametric (Mann-Whitney) tests, depending on whether the genes
 640 mRNA expression and protein present or not a normal distribution, will be used to compare
 641 the effects of treatment (liraglutide versus placebo) on the variables measured. Student's
 642 t-test will be also used to compare ultrasound measured EAT thickness before and after
 643 treatments. Continuous variables will be considered as age-adjusted, sex-adjusted and
 644 weight-adjusted means with their SDs or median, if values are skewed.

645 Univariate regression models will be performed to assess the correlation between clinical
646 variables, including echocardiographic EAT thickness and blood tests, and EAT gene and
647 protein expression. Two-tailed $p < 0.05$ indicates statistical significance.

648

649 **Data Handling and Record Keeping**

650 Each of the dedicated clinic exam rooms provides direct access to the clinical research
651 study electronic data capture (EDC) eVelos system provided by the Clinical Research
652 Informatics and Data Management Unit of the Center for Health Informatics and
653 Bioinformatics at University of Miami (UM). The investigator and research coordinator
654 will collect and manage the data.

655 Data collection records with personal identifiers will be stored in locked file cabinets, at
656 [name]. Blood samples drawn
657 and stored in conjunction with this study will not be labeled with information that could
658 directly identify study subjects. Presentation of the study results at scientific meetings or
659 in publications will not identify subjects. Access to research and confidential records will
660 be limited to clinical investigators, research coordinators, and the IRB at UM.

661 **Adipose tissue samples storing**

662 Each adipose tissue sample will be snap frozen in liquid nitrogen and stored at -80°C until
663 analysis in a freezer, in [name] lab, University of Miami, Dept of Microbiology, 1600

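### The plan does not say which test answers the between-arm hypothesis on EAT thickness, and measured baseline thickness is not used as a covariate

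*Combined protocol and SAP*

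**What the plan says.** **Hypothesis and endpoint.** Under Study Hypotheses, "EAT thickness will respond and decrease more on liraglutide" than on standard therapy. Under Endpoints, thickness is a secondary endpoint, defined as change from baseline over 3 to 12 weeks of treatment.

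**Power.** The thickness paragraph in Power Analysis opens with differences in "ultrasound measured EAT thickness, secondary endpoint, between the two study arms". It closes by claiming 80% power, with 20 per group, to "detect an expected difference of at least -20% in the EAT before and after treatment with" liraglutide. Its table gives a reference value of 9.6 mm (SD 2), with 1.9 mm detectable at 80% power and 2.88 mm at more than 99%. The baseline SD of 2 is then expected to fall to about "1.5 for the expected change. The expected change of SD will further assure significant" power.

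**Tests.** Statistical Considerations first provides for a t-test or Mann-Whitney test of "the effects of treatment (liraglutide versus placebo) on the variables measured", with the choice depending on whether gene and protein expression is normally distributed. The next sentence is the only one to assign a test to thickness by name: "t-test will be also used to compare ultrasound measured EAT thickness before and after" treatments.

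**Adjustment.** The text continues "treatments. Continuous variables will be considered as age-adjusted, sex-adjusted and" weight-adjusted means. Baseline thickness is not listed, although it is measured in every patient: "Echocardiogram for EAT thickness measurement will be performed at baseline and after" 12 weeks, whatever the arm.

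**Diet.** Study Design and the Low Calorie Diet section give a supervised diet to both arms. The latter aims at about 5% weight loss.

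**The concern.** The hypothesis compares two randomised arms, while the one test tied to thickness compares two visits. With two possible tests and no stated order, a significant fall within the liraglutide arm could be reported as the answer to the between-arm question. That fall would combine any effect of liraglutide with any effect of the diet and of time.

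The scale of the between-arm test is also open. The endpoint is worded as change, which points to a change-score test. The power table matches a test on final values. The two can differ in power, and neither makes the best use of the baseline echocardiogram that the plan already collects.

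**Working it through.** **Inputs from Power Analysis:** 20 per arm, two-sided alpha 0.05, SD 2 mm, differences 1.9 and 2.88 mm. **Assumed:** the within-arm correlation r between baseline and pre-operative thickness. The documents do not give it, so 0.3, 0.5 and 0.7 are shown. Power is from the noncentral t distribution with noncentrality = difference / SE.

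**1. Reproduce the plan's figures (two-sample t-test on final values, 38 df).** SE = 2 × √(2/20) = 0.632 mm.
- 1.9 mm: 1.9/0.632 = 3.00, power 83%.
- 2.88 mm: 2.88/0.632 = 4.55, power 99.3%.
- Detectable difference at 80% power: 1.82 mm.

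Both stated figures are met.

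**2. Does the before/after contrast fit the table?** For a paired test in one arm of 20, with SD 2 at both visits, the SD of change is 2√(2(1−r)). At 1.9 mm, power is 81% if r = 0, and 93%, 98% and 99.9% at r = 0.3, 0.5 and 0.7. The 80%-power detectable differences at those three values of r are 1.56, 1.32 and 1.02 mm. The table therefore fits a paired test only if r is near zero, and fits the between-arm test without any such condition.

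**3. What each contrast estimates.** The expected fall within the liraglutide arm is diet and time effect + liraglutide effect. In the placebo arm it is diet and time effect alone. If the diet acts alike in both arms, the between-arm difference leaves the liraglutide effect and the within-arm change does not. No numerical assumption is needed.

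**4. Between-arm power at 1.9 mm, SD 2 at both visits.**
- Change score: SE = 2√(2(1−r)) × √(2/20), 38 df.
- ANCOVA: SE = 2√(1−r²) × √(2/20 × (1 + 1/36)), 37 df. The factor 1 + 1/36 allows for the expected chance imbalance in baseline.

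| r (assumed) | Final value, unadjusted | Change score: SE, power | ANCOVA: SE, power |
|---|---|---|---|
| 0.3 | 83% | 0.748, 70% | 0.612, 86% |
| 0.5 | 83% | 0.632, 83% | 0.555, 91% |
| 0.7 | 83% | 0.490, 97% | 0.458, 98% |

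**5. The plan's 1.5 mm.** The text does not make clear which SD this is.
- As the follow-up SD in both arms: the final-value t-test has SE 1.5 × √(2/20) = 0.474, noncentrality 1.9/0.474 = 4.01 and power 97%. ANCOVA gives 98%, 99% and more than 99%. Change scores give 79%, 90% and 98%.
- As the SD of change: the same arithmetic gives the change-score test 97%. The implied r is (4 + 4 − 2.25)/8 = 0.72 if follow-up SD is 2, or (4 + 2.25 − 2.25)/6 = 0.67 if it is 1.5.

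In each case one simple unadjusted test is already at 97%, so ANCOVA can add at most 3 points to it.

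**The case against.** The strongest reply is that the between-arm test is already there. Thickness is one of the variables measured, the general sentence compares liraglutide with placebo on those variables, and the word for *also* in the following sentence makes the before/after test an addition. The hypothesis, the opening of the power paragraph and the power table are all between-arm. This largely stands. A reader might infer that the plan has no between-arm test of thickness, and the documents do not support that. What remains is that the general sentence does not name thickness, ties its choice of test to gene and protein data and leaves the scale open, while the closing power sentence describes the before/after contrast.

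A second reply is that ANCOVA is only an efficiency preference. A between-arm change-score test is indeed valid, and so is a final-value test. Under either reading of the 1.5 mm, the gain over the better-suited unadjusted test is small. It would be wrong to present the gain as large in general: at SD 2 and r = 0.3 it is 16 points over change scores (86 − 70) but only 3 over final values (86 − 83). The argument for ANCOVA is that it settles the scale and does well across all these cases at no cost.

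A third reply is that nothing in the plan says a within-arm result will be presented as the answer. That is correct. The point is that the plan leaves the choice open until after the data are seen.

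**Conclusion.** The point holds as a specification gap with a free improvement in method. The plan does not say which contrast, or which scale, answers the thickness hypothesis, and it leaves out a prognostic baseline value that it measures in everyone.

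A reader might also infer that the trial is underpowered for thickness or that the table is wrong. Neither follows: 83% and 99.3% reproduce the stated figures for a between-arm comparison of final values, and the sample size is unaffected.

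The benefit of baseline adjustment ranges from about 1 point (98% against 97% for change scores at r = 0.7) to about 16 points (86% against 70% at r = 0.3), with SD 2 at both visits. It is small against the better unadjusted test if 1.5 mm is either the follow-up SD or the SD of change. These figures rest on an assumed r and on all 20 patients per arm contributing both echocardiograms. The endpoint is secondary, so the change is advisable rather than essential.

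**What to change.** 1. In Statistical Considerations, replace the before/after sentence with: *Pre-operative EAT thickness will be compared between arms by ANCOVA with arm and baseline thickness as terms; the adjusted difference (liraglutide minus placebo) and its 95% CI answer the thickness hypothesis; within-arm before/after changes are descriptive only.*

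2. State that the age-, sex- and weight-adjusted means in the sentence that follows are supportive and not part of this model. Otherwise the two sentences would conflict over which adjusters apply to thickness.

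3. In the closing sentence of the thickness power paragraph, change the contrast from before/after on liraglutide to a difference in EAT thickness between the two study arms. Keep the stated 80% and >99%. Add no power figures that depend on an assumed correlation.

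The cost is wording only. The baseline echocardiogram is already planned in all patients, and no visit, patient or stated power figure changes.
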